6.2 Dose Reduction Criteria for Non-Hematologic Toxicity at Least Possibly Related to Erlotinib

Toxicity (NCI CTCAE v4.0)	Dose Modification^a
Diarrhea	
Grade 1 or 2	None. May initiate therapy with loperamide or alternate antidiarrheal. See Section 6.3 for treatment details.
Grade 3 ^b or 4 ^b	^{a)} Interrupt erlotinib until resolution to \leq grade 2 and then restart 1 dose level lower. If the event does not resolve to \leq grade 2 within 14 days, erlotinib will be discontinued.
Rash	
Grade 1	None
Grade 2	None. Initiate treatment as outlined in Section 6.3. If rash persists and is intolerable or worsens over 10 – 14 days, then reduce by 1 dose level.
Grade 3 ^b	Reduce by 1 dose level. If rash persists or worsens over 10 – 14 days, then interrupt erlotinib until resolution to \leq grade 2 and then restart 1 dose level lower. If the event does not resolve to \leq grade 2 within 14 days, erlotinib will be discontinued.
Grade 4	Permanently discontinue erlotinib.
Interstitial Lung Disease (ILD)	
Any Grade	If ILD possibly related to study drug is suspected, erlotinib should be interrupted immediately pending diagnostic evaluation. If ILD is diagnosed, erlotinib should be discontinued permanently and appropriate treatment instituted as necessary.
Other Non-Hematologic Toxicities	
Grade 1 or 2	None
Grade 3 ^{b, c}	Interrupt erlotinib until resolution to \leq grade 2 and then restart 1 dose level lower.
Grade 4	Permanently discontinue erlotinib

a) Doses that have been reduced 1 dose level for toxicity may be re-escalated to the previous

dose level only if the toxicity abates or returns to baseline severity and the investigator believes it is in the best interest of the patient. Doses that have been reduced 2 dose levels for toxicity may only be re-escalated to the previous dose level (ie, dose level at first reduction) and only if the toxicity abates or returns to baseline severity and the investigator believes it is in the best interest of the patient. Doses that have been reduced 2 or more dose levels for toxicity may not be re-escalated to the starting dose level (or dose-escalated dose for tobacco smokers). Any patient who fails to tolerate treatment at 50 mg/day will be discontinued from the study.

- b) If not responding to optimal treatment within 48 hrs.
- c) Only if ≥ 2 grade level change from baseline

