6.3 Suggested Management of Toxicity: The following guidelines are offered as suggestions for the management of toxicity. Variations of these are acceptable based on the patient's individual circumstances and physician preference.

If a patient experiences several toxicities, dose adjustments are to be made based on the greatest degree of toxicity (ie, reducing the dose to the lowest level). If significant toxicity is still apparent, the dose may be reduced a second time. Any patient who fails to tolerate treatment of 50 mg/day will be withdrawn from the study.

Antidiarrheal and antirash medications may be introduced at any time if clinically indicated. Previous phase 1 and 2 studies have demonstrated that the frequency and severity of diarrhea can be managed with loperamide. The recommended dose of loperamide is 4 mg at first onset, followed by 2 mg every 2 to 4 hours until diarrhea resolves for 12 hours. Other antidiarrheal medications may be used as clinically indicated.

In the event of severe or persistent diarrhea, nausea, anorexia, or vomiting associated with dehydration due to erlotinib therapy, erlotinib should be interrupted and appropriate measures should be taken to intensively treat the dehydration.

Patients may be informed that skin toxicity is to be expected during treatment with erlotinib. Skin toxicity may take the form of dry skin, rash, acneiform eruption, or hair or nail changes. Prophylactic treatment of the skin may prevent or reduce skin toxicity. The patient should be encouraged to use an alcohol-free, emollient cream applied twice a day to the entire body as soon as the patient starts therapy with erlotinib. Creams and ointments are recommended because they have a greater ability to retain moisture than lotions. Examples of suitable emollient creams include: Neutrogena® Norwegian formula, SARNA® Ultra, Vanicream™, Aveeno® (fragrance-free formulation), and Eucerin® cream. Other over-the-counter aqueous creams or emulsifying ointments may also provide symptomatic benefit. Lotions are not recommended because they often contain alcohol, which may dry the skin. Patients may also be encouraged to use a titanium dioxide or zinc oxide-based sunscreen product applied to sun-exposed areas twice per day.

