Patients who develop skin toxicity and are symptomatic may be treated with topical therapy such as hydrocortisone cream or clindamycin gel. If needed, oral minocycline or oral doxycycline may be combined with the topical therapy. A topical immodulating cream such as Elidel could also be considered. For more severe rash, oral corticosteroids may be beneficial. Patients who fail to respond to these measures may have the dose of erlotinib interrupted or reduced. See Annex 5 for more information on skin toxicity management.

Minocycline may interfere with anticoagulants and oral contraceptives. Patients treated with minocycline who are taking anticoagulants and/or oral contraceptives should be monitored accordingly.

There have been infrequent reports of serious ILD, including fatal events, in patients receiving erlotinib for the treatment of NSCLC and other advanced solid tumors. In the event of acute onset of new or progressive, unexplained pulmonary symptoms such as dyspnea, cough, and fever, where ILD is suspected, study drug should be interrupted pending diagnostic evaluation. If ILD is diagnosed, study drug should be permanently discontinued and appropriate treatment instituted as necessary.

Treatment with erlotinib should be used with extra caution in patients with total bilirubin $> 3 \times$ ULN. Patients with hepatic impairment (total bilirubin $>$ ULN or Child-Pugh A, B and C) should be closely monitored during therapy with erlotinib.

Gastrointestinal perforation (including fatalities) has been reported in patients receiving erlotinib. Patients receiving concomitant anti-angiogenic agents, corticosteroids, NSAIDs, and/or taxane-based chemotherapy, or who have prior history of peptic ulceration or diverticular disease are at increased risk. Permanently discontinue erlotinib in patients who develop gastrointestinal perforation.

Bullous, blistering and exfoliative skin conditions have been reported, including cases suggestive of Stevens-Johnson syndrome/toxic epidermal necrolysis, which in some cases were fatal. Interrupt or discontinue erlotinib treatment if the patient develops severe bullous, blistering, or exfoliating conditions.

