Ocular Disorders, including corneal perforation or ulceration have been reported during use of erlotinib. Other ocular disorders including abnormal eyelash growth, keratoconjunctivitis sicca or keratitis have been observed with erlotinib treatment and are known risk factors for corneal ulceration/perforation. Interrupt or discontinue erlotinib therapy if patients present with acute/worsening ocular disorders such as unexplained eye pain.

Erlotinib dosing should be discontinued for any severe toxicity that does not respond to treatment or failure to recover within 14 days from hematological toxicity attributable to erlotinib.

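### The section 6.2 dose table has no gastrointestinal perforation row, so below grade 4 it disagrees with the permanent stop in section 6.3, and no text says which governs

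*Combined protocol and SAP*

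**What the plan says.** The table in section 6.2 sets dose changes for non-hematologic toxicity at least possibly related to erlotinib. It names diarrhea, rash and ILD, and sends everything else to a row for other non-hematologic toxicities. That row gives no change at grade 1 or 2 and permanent discontinuation at grade 4. At grade 3 it says to interrupt until the event is no worse than "grade 2 and then restart 1 dose level lower". Two footnotes restrict the grade 3 entry. Footnote b reads "If not responding to optimal treatment within 48 hrs", and footnote c requires a change of at least two grades from baseline.

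Section 6.3 contains the only sentence on what to do about perforation: "Permanently discontinue erlotinib in patients who develop gastrointestinal perforation". It has no limit by grade or attribution. The section opens with "The following guidelines are offered as suggestions for the management of toxicity" and continues "Variations of these are acceptable based on the patient's individual circumstances and physician preference". Its last paragraph adds a general stop: "Erlotinib dosing should be discontinued for any severe toxicity that does not respond to treatment".

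ILD is handled in both places. The 6.2 table says "If ILD is diagnosed, erlotinib should be discontinued permanently and appropriate treatment instituted as necessary", and 6.3 says "If ILD is diagnosed, study drug should be permanently discontinued and appropriate treatment instituted as necessary".

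**The concern.** A physician or research nurse who looks up a related perforation in the dose table finds no entry and lands in the catch-all row. At grade 3 that row describes a path back to treatment, and at grade 1 or 2 it asks for nothing. Section 6.3 tells the same reader to stop for good. Both instructions cannot be followed, and the one that stops treatment sits in the section labelled as suggestions.

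At stake is re-exposure to erlotinib after an event that the protocol itself lists as sometimes fatal. The treatment of ILD, with the stop written in both sections, suggests that the perforation stop was simply not carried into the table.

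**Working it through.** The plan gives no figure on this point. The check is a comparison of texts, followed by an estimate of frequency.

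**1. Action for an erlotinib-related perforation, by grade**

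| Grade | 6.2 table (catch-all row) | 6.3 | Agree? |
|---|---|---|---|
| 1–2 | No change | Permanent stop | No |
| 3 | Interrupt to grade 2 or lower, restart one level lower (footnotes b, c) | Permanent stop | No |
| 4 | Permanent stop | Permanent stop | Yes |

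**2. Do the footnotes close the gap?** Footnote c is met by a new grade 3 perforation with none at baseline. Footnote b limits the grade 3 action to events that have not responded within 48 hours. Read literally, a grade 3 perforation that does respond in that time needs no interruption at all, which is further from 6.3. The diarrhea row and the grade 3 rash entry require discontinuation if the event has not settled within 14 days. The catch-all grade 3 entry has no such limit.

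**3. Does other text close it?** The general stop at the end of 6.3 covers severe toxicity that does not respond to treatment. It may catch some events that meet footnote b. It does not clearly reach a perforation that is treated and later falls to grade 2 or lower, which is the table's condition for restarting, and it too sits in 6.3. The table refers to 6.3 only for treating diarrhea and rash. No sentence ranks the sections.

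**4. How often could it arise?** Inputs from section 2.1.1: 37 serious perforation events assessed as related, 14 of them fatal, and more than 22,000 people estimated to have received erlotinib. Input from section 11.0: 29 patients.

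- Fatal share: 14/37 = 38%. For ILD and related lung events in the same table it is 198/621 = 32%.
- Non-fatal events, the only ones where re-dosing could arise: 37 − 14 = 23.
- Rate: 23/22,000 = 10.5 per 10,000.
- Expected in this trial: 29 × 23/22,000 = 0.030.
- Chance of at least one: 1 − exp(−0.030) = 3.0%.
- Exact Poisson 95% interval for a count of 23: 14.58 to 34.51. Multiplied by 29/22,000, this is 0.019 to 0.045 expected events.
- Matching chances of at least one: 1 − exp(−0.0192) = 1.9% and 1 − exp(−0.0455) = 4.4%.

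The 23 events are not split by grade. They include any grade 4 events, where the sections agree, so under the stated assumptions the figure is an upper limit for serious events in the disputed grades. Perforations not reported as serious are not in it.

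**5. Does the trial design depend on it?** The response endpoint and two-stage rule in section 11.0 do not use the dose table. The toxicity rule in section 11.1 counts clinically significant, related grade 3 or 4 non-hematologic events, whatever dosing action follows. Neither changes.

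**The case against.** The strongest reply is that the stop already exists. The 6.3 sentence is direct and names the event, while the competing text is a residual row that never mentions perforation. Ordinary reading puts the specific over the general, and the table itself sends readers to 6.3 twice. The suggestions label is also not special to 6.3: section 5.2 describes the whole treatment plan as suggested guidelines, and dose changes outside its dose-level table are allowed after discussion with the PI or Co-PI. The restart path is narrow because of footnote b, and it partly overlaps the general stop for non-responding toxicity.

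Most of this stands, and it is why the practical effect is small. It does not remove the conflict. The argument from specificity is sensible, but the protocol does not state it, and the general stop covers only part of the ground.

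Two stronger readings are tempting, and the documents support neither. A reader might infer that the 6.2 table is binding and overrides an optional 6.3, so that the protocol requires re-dosing after perforation. No text ranks the sections, and section 5.2 weakens any claim that 6.2 is the mandatory one. A reader might also take the 38% fatal share as the risk run by a re-dosed patient. It is the share of listed events that were fatal. Those patients could not be re-dosed, and the documents give no recurrence risk for survivors.

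**Conclusion.** The inconsistency is real and covers grades 1 to 3. For a related perforation the table permits continuing or restarting erlotinib where 6.3 says to stop for good. It should be corrected, but it is a low-frequency safety matter and not a flaw in the trial's inference.

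Its size is about 0.03 non-fatal serious events in 29 patients, or roughly a 3% chance of one. The interval reflects count error only. The estimate rests on full reporting, one event per patient, exactly 22,000 exposed (the protocol says more, which would lower the rate slightly) and AML risk equal to that of the pooled population. The last assumption is uncertain: section 6.3 lists corticosteroids among the perforation risk factors and also says oral corticosteroids may help with more severe rash.

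**What to change.** Add one row to the 6.2 table, parallel to the ILD row: *Gastrointestinal perforation, any grade: permanently discontinue erlotinib.* Keep the 6.3 sentence as it stands. The table covers only toxicity at least possibly related to erlotinib, so 6.3 is still needed for perforations not attributed to the drug.

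I would not add a similar row for eye disorders. Section 6.3 says to interrupt or discontinue for acute or worsening eye disorders, where the table asks for nothing at grade 1 or 2. But a row copying that wording for all grades would drop the table's defined grade 3 rule for restarting.

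The cost is one table row, with no added visits, tests or patients and no change to sample size or stopping rules.

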6.4 Dose Escalation

Patients who have had a prior dose reduction of erlotinib and who have no toxicity for at least 1 month of therapy may increase the dose of erlotinib provided they have experienced no grade ≥ 3 erlotinib-related toxicity. Dose escalation may be done by one dose level at a time and dose escalations should not be done more often than every 28 days. Patients may not escalate to a dose level they received earlier where the patient experienced grade 4 toxicity.

6.5 Supportive Care Guidelines

Supportive measures including erythropoietin, analgesics, blood transfusions, antimicrobials, and hematopoietic colony stimulating factors for treatment of cytopenias are permitted.

Prophylactic use of hematopoietic colony stimulating factors is not permitted.

Other chemotherapy, investigational cytotoxic agents, radiation, or biologic therapy is prohibited while the patient is on study with the following exceptions during cycle 1: During the first 7 days of study only, patients may receive leukaphereses to control elevated blast and/or platelet counts and hydroxyurea is allowed for a maximum of the first 28 days on study. Intrathecal chemotherapy to treat isolated CNS involvement of leukemia is allowable.

6.6 Patients may be taken off study at any time to receive a stem cell transplant as clinically indicated.

7.0 AGENT FORMULATION AND PROCUREMENT

7.1 Formulation

The pharmaceutical preparations of erlotinib are formulations containing the hydrochloride salt. Erlotinib is supplied as tablets containing erlotinib hydrochloride equivalent to 150 mg, 100 mg, and 25 mg of erlotinib. All tablets are round, white, film-coated, bi-convex tablets without markings. Additional information regarding erlotinib can be found in the Tarceva Package Insert. Erlotinib for this trial will be provided as investigational product.

7.2 Packaging and Labeling

Erlotinib tablets are supplied in blue-white, high-density polyethylene (HDPE) bottles of 30 tablets each.

7.3 Storage and Handling

Erlotinib tablets should be stored at 25°C (77°F); excursions permitted to 15° - 30°C (59° - 86°F).

7.4 Administration

Erlotinib tablets should be taken at approximately the same time of day. Each erlotinib dose is to be taken with up to 200 mL (~ 1 cup or 8 oz) of water, and should be taken 1 hour before or 2 hours after meals. Erlotinib should not be taken with grapefruit or grapefruit juice. The entire dose must be taken at one time. If the patient vomits after taking the tablet(s), the dose is replaced only if the tablet(s) can actually be seen and counted. Missed doses will not be made up. Unused study drug returned by patients should be destroyed in accordance with the institution's policy. Patients will document self-administration by using the MDACC pill diary.

8.0 PATIENT EVALUATION

8.1 Pre-Treatment Evaluation: All pretreatment studies should be obtained within 14 days (± 3 days) of entry into the trial, unless otherwise stated.

8.1.1 A complete history and physical, including assessment of baseline adverse events.

8.1.2 CBC, platelet count, differential (differential can be omitted if WBC is $\leq 0.5 \times 10^9/L$).

8.1.3 Creatinine, total bilirubin, ALT.

8.1.4 Pregnancy test (urine or plasma) in females of childbearing potential should be performed within 14 days of initiation of study.

8.1.5 Bone marrow aspirate during the last 14 days preceding study initiation. Cytogenetics will be obtained prior to therapy (results from prior analysis can be used for this purpose).

8.1.6 Pretreatment optional correlative studies (Appendix A). Every effort will be made to collect all samples at all time points for all patients; however, missing collection in one or more of these time points in occasional patients will not be considered a protocol deviation/violation.

8.1.7 Chest x-ray

8.2 Evaluation During Treatment: All tests are ± 5 days unless otherwise specified.

8.2.1 Physical exam after 28 days of therapy (± 7 days), then every 2-3 months.

8.2.2 Assessment of adverse events.

8.2.3 CBC, platelet count, differential once weekly for the first 3 months, then every 2-4 weeks (differential can be omitted if WBC is $\leq 0.5 \times 10^9/L$) until 6 months of therapy, then every 6-8 weeks.

8.2.4 Creatinine, total bilirubin, ALT weekly for the first 3 months, then every 2-4 weeks until 6 months of therapy, then every 6-8 weeks.

8.2.5 Bone marrow aspiration on day 28 (± 7 days), then every 2-3 months for 1 year; then as clinically indicated. Bone marrow aspirations to be performed at MDACC.

8.2.6 Correlative studies (Appendix A). Every effort will be made to collect all samples at all time points for all patients; however, missing collection in one or more of these time points in occasional patients will not be considered a protocol deviation/violation.

8.2.7 For patients that remain on study with no significant toxicity for more than 12 months, subsequent evaluations during study may be modified after discussion with the principal investigator. These include a decrease in frequency of correlative studies and other laboratory tests to once every one to three cycles.

8.2.8 For patients receiving concomitant warfarin, PT at least every 4 weeks for the first 6 months or more frequent if clinically indicated; after the first 6 months, PT as clinically indicated.

8.3 End of Treatment Visit

8.3.1 To be completed 30 days ($+/- 7$ days) after the last dose of study drug.

8.3.2 This visit will consist of a review of symptoms and adverse events. This visit can be done by phone if patient unwilling or unable to do at MDACC.

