- Unless otherwise noted, the electronic SAE application (eSAE) will be utilized for safety reporting to the IND Office and MDACC IRB.
- Serious adverse events will be captured from the time of the first protocol-specific intervention, until 30 days after the last dose of drug, unless the participant withdraws consent. Serious adverse events must be followed until clinical recovery is complete and laboratory tests have returned to baseline, progression of the event has stabilized, or there has been acceptable resolution of the event.
- Additionally, any serious adverse events that occur after the 30 day time period that are related to the study treatment must be reported to the IND Office. This may include the development of a secondary malignancy.

Reporting to FDA:

- Serious adverse events will be forwarded to FDA by the IND Sponsor (Safety Project Manager IND Office) according to 21 CFR 312.32.

It is the responsibility of the PI and the research team to ensure serious adverse events are reported according to the Code of Federal Regulations, Good Clinical Practices, the protocol guidelines, the sponsor's guidelines, and Institutional Review Board policy.

Investigator Communication with Supporting Company:

Serious adverse event will be reported by FAX concurrently to OSI Drug Safety ([contact]). Information not available at the time of the initial report (e.g., an end date for the adverse event or laboratory values received after the report) must be documented on a follow-up report. A final report to document resolution of the SAE is required. **Hospitalizations for the management of any expected adverse events (previously described) will not have an expedited report but it will be included in the annual report via the SAE log.**

Pregnancies: Any pregnancy that occurs during study participation or within 4 weeks of the patient's last study drug administration should be reported using the MD Anderson SAE Form. To ensure patient safety each pregnancy must also be reported to OSI and the IND Office within 24 hours of learning of its occurrence.

The Investigator will follow the pregnant female until completion of the pregnancy. The Investigator will provide this information as a follow-up to the initial SAE.

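### The only scheduled post-treatment safety contact (8.3.1) may fall up to 7 days before the SAE capture window in 10.4 closes

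*Combined protocol and SAP*

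**What the plan says.** All references are to the combined protocol and SAP.

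- **Timing of the contact (8.3.1):** "To be completed 30 days ($+/- 7$ days) after the last dose of study drug".
- **Content (8.3.2):** "This visit will consist of a review of symptoms and adverse events". A phone call is acceptable when the patient cannot or will not attend. No pregnancy test or question is listed.
- **SAE window (10.4):** "Serious adverse events will be captured from the time of the first protocol-specific intervention, until 30 days after the last dose of drug", unless consent is withdrawn.
- **Later SAEs (10.4):** "any serious adverse events that occur after the 30 day time period that are related to the study treatment must be reported to the IND" (its office is the recipient). No contact is scheduled to find them.
- **Pregnancy window (10.4):** the reporting duty covers pregnancies on study or "within 4 weeks of the patient's last study drug administration", with a 24-hour deadline that starts when the site learns of the pregnancy.
- **Other scheduled adverse event review:** after the baseline assessment in 8.1.1, the only other item is "8.2.2 Assessment of adverse events", which belongs to the evaluations during treatment (8.2). Section 8 ends with 8.3.

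**The concern.** The tolerance in 8.3.1 is symmetric around the day on which the SAE window in 10.4 closes. The early half of the tolerance therefore lies inside the window that the contact is meant to cover. A site can hold the contact on day 23, satisfy 8.3, and have no planned means of meeting 10.4 for days 24 to 30.

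The other post-treatment duties in 10.4 do not find new events. Following an SAE to resolution, or a pregnancy to completion, presupposes that the event is known. The reporting deadlines run from the time the site learns of the event.

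Safety and tolerability is a primary objective (1.1.2), and at most 29 patients are enrolled (11.0). An early contact can omit late events but cannot add any, so any error is toward fewer late SAEs. Ascertainment is also unequal: a patient contacted on day 23 and one contacted on day 37 are treated as having been followed for the same window.

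**Working it through.** The plan states no figure for this gap, so there is none to reproduce.

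**Inputs from the documents**
- Contact: day 30, tolerance 7 days either way (8.3.1)
- End of SAE window: day 30 (10.4)
- End of pregnancy window: 4 weeks = day 28 (10.4)
- Maximum enrolment: 29 (11.0)

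**Step 1. Permitted contact days.** Earliest 30 − 7 = 23; latest 30 + 7 = 37. That is 15 permitted days.

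**Step 2. Uncovered tail.** Gap = max(0, end of window − day of contact).

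| Day of contact | SAE gap (days) | Pregnancy gap (days) |
|---|---|---|
| 23 | 7 | 5 |
| 24 | 6 | 4 |
| 25 | 5 | 3 |
| 26 | 4 | 2 |
| 27 | 3 | 1 |
| 28 | 2 | 0 |
| 29 | 1 | 0 |
| 30 to 37 | 0 | 0 |

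The largest SAE gap is 7/30 = 23% of the window. The largest pregnancy gap is 5/28 = 18%. Of the 15 permitted days, 8 leave no SAE gap. If contacts were spread evenly over the 15 days, the mean SAE gap would be (7+6+5+4+3+2+1)/15 = 28/15 = 1.9 days.

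**Step 3. Patients who could be affected.** This step needs a post-treatment SAE risk, which the documents do not give. I assume a 30-day risk R of 20% to 50% and a constant hazard. The probability that a patient's first post-treatment SAE falls after a contact on day d, but by day 30, is

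(1 − R)^(d/30) − (1 − R).

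*Every contact on day 23:*
- R = 20%: 0.843 − 0.800 = 0.043; × 29 = 1.2 patients
- R = 50%: 0.588 − 0.500 = 0.088; × 29 = 2.5 patients

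*Contacts spread evenly over days 23 to 37:* sum the formula over d = 23 to 29 (later days contribute zero) and divide by 15.
- R = 20%: 0.170/15 = 0.0113; × 29 = 0.3 patients
- R = 50%: 0.343/15 = 0.0229; × 29 = 0.7 patients

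Both scenarios assume that no event in the tail comes to light by another route, so they are upper figures for their visit pattern. They count patients with a first SAE in the tail, not repeat events.

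**Step 4. After the change.** If the contact cannot precede day 30, the SAE gap is 30 − 30 = 0. The date then also lies beyond day 28, but 8.3.2 lists nothing that would reveal a pregnancy.

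**The case against.** The strongest reply is that 10.4 stands on its own. It requires SAE capture to day 30 whatever the date of the 8.3 contact, makes the investigator and research team responsible for reporting, and extends to related SAEs after day 30. A reader might infer that a site closing a patient on day 23 complies fully and that a missed event breaks no rule. The documents do not support that: stopping capture on day 23 fails 10.4. Learning of the event starts the reporting deadlines; it does not shorten the capture period. What remains is a gap in scheduled prompting, not in obligation.

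Three further replies have force.

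- **Unseen procedures.** Section 10.4 defers to an institutional review board policy and sponsor guidelines that are not in the documents. These might prompt a later check, so one can say only that the protocol itself schedules none.
- **No named statistic is biased.** A reader might infer that a 30-day SAE count or death rate, as a planned output, would be distorted. Section 11.2 names neither. It lists treatment-emergent adverse events by severity and relationship, events leading to discontinuation, and laboratory summaries.
- **Ordinary tolerance.** The same 7 days either way is used in 8.2.1 and 8.2.5, and more than half of the permitted contact days leave no gap.

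These replies limit the weight of the point. They do not remove the mismatch: within the protocol, the last scheduled contact may precede the end of the window it serves.

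**Conclusion.** The point holds as a minor one. Contacts on days 23 to 29 leave the last 1 to 7 days of the SAE window without scheduled ascertainment; contacts on days 30 to 37 leave none. The consequence is confined to the completeness of late safety data and runs toward under-counting. The response endpoint is unaffected, as is the toxicity rule in 11.1, which concerns the first 28 days.

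The size is unknown. The even-spread result of 0.3 to 0.7 of 29 patients rests on an assumed risk, a constant hazard and an assumed visit pattern. A reader might take the day-23 result of 1.2 to 2.5 as the expected loss. It is a ceiling under the same assumed risks, because it also needs every visit on the earliest permitted day and no other discovery of events.

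Two inferences about pregnancy should also be resisted. The gap there is at most 5 days, not a week. And moving the date alone does not secure the 4-week window, because 8.3.2 asks nothing about pregnancy.

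**What to change.** Either change closes the SAE gap:

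- make the tolerance in 8.3.1 one-sided, so that the contact falls on day 30 to day 37 after the last dose; or
- keep the present tolerance and require a phone contact on or after day 30 for any patient seen earlier. Section 8.3.2 already accepts phone contact.

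To serve the pregnancy window as well, add a pregnancy question to the content of this contact in 8.3.2.

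The cost is a short wording amendment and slightly less scheduling flexibility. The second option adds a phone call for patients seen early.
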